	
faculty as requiring a single tooth extraction
 
 • A dental implant is indicated and treatment planned to replace the missing tooth • Have adequate restorative space for a dental implant-retained restoration • Have at least 10mm of alveolar bone height, without impinging on the maxillary sinus or inferior alveolar canal. • Have a dehiscence of the buccal or lingual bony plate of the tooth socket extending no more than 50% of the total depth of the socket. • Female patients who have undergone a hysterectomy, tubal ligation, or menopause, and non-pregnant women of child-bearing potential. • Are nonsmokers or former smokers. Current smokers may be included if they smoke ≤ 10 cigarettes per day 	
 • Patients will not be entered who are mentally incompetent, prisoners, or pregnant. • Pregnant women or women intending to become pregnant during the study period (as confirmed verbally; an over the counter pregnancy test will be provided if pregnancy status is unknown or suspected). • Patients who become pregnant during the study will be withdrawn and standard care will be delivered. • Smokers who smoke >10 cigarettes per day • Clinical and/or radiographic determinations which will preclude inclusion in this study are: Active infection other than periodontitis; Inadequate bone dimensions or restorative space for a dental implant; Presence of a disease entity, condition or therapeutic regimen which decreases probability of soft tissue and bony healing, e.g., poorly controlled diabetes, chemotherapeutic and immunosuppressive agents, autoimmune diseases, history of bisphosphonate use or long-term steroid therapy; Positive medical history of endocarditis following oral or dental surgery.

6.4. Will screen failures be allowed to re-screen at a later date?
	
 No  Yes If yes, describe criteria below ↓
 
Subjects who do not meet inclusion criteria initially may be re-screened and included in the study if inclusion criteria is met at a later date
	

7. Study Intervention(s) being tested or evaluated

This can include prevention, diagnostic or therapeutic interventions (e.g., drug or device) or educational, health services or basic science interventions (e.g., educational program, health care delivery model, or examining basic physiology)

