8.8 Description of Methods (or include in separate document)

Check to indicate that the Methods are described in an attached file →

Each extraction socket will receive one 5 X 5 X 8mm or 5 X 5 X 10mm graft cube (research) with no attempt to fill the entire socket. No wound dressing or membrane will be used to cover the bone graft material as both materials can be used alone. All extraction sockets will be sutured with Vicryl 4.0 mattress suture which will be removed approximately 2 weeks (\pm 1 week) after the procedure as per standard of care. All patients will be prescribed an oral antibiotic after the procedure either Amoxicillin 500mg three times per day for 7 days, or if they are allergic to penicillin/amoxicillin they will be prescribed Clindamycin 300mg three times per day for 7 days as per standard of care.

In keeping with the protocol our study group has used several times before, the plan will be to extract non-molar teeth and graft with the test/control materials. Each subject will provide a single non-molar tooth site for study treatment. Following approx. 14 weeks of healing, we will harvest a core biopsy at the time of implant placement. The core biopsy will then be evaluated for the primary outcomes: % vital bone formation, % residual graft material, and % "CT/other" (fibrous tissue and marrow space). We will also evaluate the following secondary outcomes using a custom measuring stent for each subject: change in ridge width; change in buccal ridge height, and change in lingual ridge height. During the 14-week healing period, subjects will be followed up with biweekly and monthly visits as per standard of care, to evaluate healing.

A detailed visit by visit outline is provided below:

Step-by-Step Methods: All the procedures are routinely performed in the graduate periodontics clinic as part of standard care. The methodology is the same previous studies of our group HSC20130470H, HSC20150708H, HSC20170339H, HSC20170267H, among others.

Visit 1 - Screening examination:

If a patient presents at a consultation appointment at the graduate periodontics clinic with a non-molar tooth (incisors, canines, premolars) that needs to be extracted and replaced with a dental implant, the treating doctor will provide:

- Explanation to the patient of the purposes of the study and the planned procedures related to the study.
- Explanation to the patient of the risks, benefits and possible complications of participation in the study.

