One measurement stent will be fabricated to facilitate clinical ridge measurements. A clear suck-down resin measuring stent will be fabricated in the laboratory to allow standardization of the location of clinical measurements of ridge width and height through small holes that will be placed in the stent at the time of tooth extraction.

The width of keratinized tissue will be recorded clinically to the nearest 0.5mm using a periodontal probe at the mid-buccal and mid-lingual sites of the tooth to be extracted.

A pre-operative periapical radiographic image will be taken before the extraction as per standard of care (if not already available).

At the time of surgery, local anesthesia will be administered. Conscious sedation will be administered according to patient need and investigator preference, per standard care. Buccal and lingual flaps will be minimally reflected to a point up to 3mm apical to the bony crest.

Prior to tooth extraction, the clinical measuring stent will be placed and measurements of ridge width and ridge height will be taken and recorded to the nearest 0.5mm. Ridge width will be measured to the nearest 0.5mm using a ridge caliper at a point approximately 4mm apical to the facial and lingual bony crest through small holes created in the stent at those locations. Ridge height will be measured to the nearest 0.5mm through two holes in the occlusal aspect of the stent – one hole directly above the facial bony crest and another hole directly above the lingual bony crest. This stent will be retained for use during the subsequent implant placement surgery.

Tooth extraction will be performed as atraumatically as possible. Following tooth extraction, a final determination of enrollment into the study will be conducted based on the integrity of the buccal bone wall plate at the extraction site. If the buccal plate is intact, defined as no bony dehiscence greater than 50% of the socket depth, the patient will remain enrolled in the study.

Conversely, if the buccal plate integrity has not been maintained (bony dehiscence >50%) the patient will be exited from the study and standard care therapy will be delivered to the patient.

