After extraction, the number of bony walls in each socket will be recorded along with the presence of any bony dehiscences or fenestrations. Buccal and lingual flap elevation will be minimized and will extend no more than 2-3mm beyond the bony crest on the facial and lingual surfaces. The buccal plate thickness will be measured using an Iwanson gauge positioned perpendicular to the inner wall of the extraction socket. One beak of the gauge will be placed within the extraction socket 1.0mm apical to the alveolar bone crest. The other beak will be placed on the external bone surface. This buccal plate thickness measurement will be recorded to the nearest 0.1 mm.

The socket will be thoroughly debrided, a 5 X 5 X 8 mm or 5 X 5 X 10 mm bone graft cube of either 90% bovine derived xenograft granules and 10% porcine collagen (Bio-Oss® Collagen, Geistlich, Inc.) or a resorbable sponge-like matrix of 80% hydroxyapatite and 20% sugar cross-linked porcine collagen (Ossix™ Bone, Datum Dental Ltd) will be soaked in patient's blood and inserted in the socket. No attempt will be made to completely fill the socket as the materials expand after they contact fluids. No membrane or wound barrier will be placed over the graft in either group. Vicryl 4.0 sutures will be placed over the graft material to secure it in place as part of standard of care. Primary closure will not be attempted.

Visit 3 - Post-operative visit

The post-operative visit after extraction/ridge preservation will be scheduled approximately 3 weeks (± 1 week) after the procedure. If needed, an optional POT visit may be scheduled before this visit, per standard care and as determined by patient need.

Visit 4 - Pre-implantation:

Approximately 3 months after the extraction (\pm 2 weeks) a CBCT of the prospective implant site may be taken as needed per standard care. The implant surgery will ensue within 2 weeks (\pm 2 weeks). The CBCT is not part of the study but rather standard of care.

Prior to surgery, pregnancy status will be confirmed verbally. An over the counter pregnancy test will be provided if pregnancy status is unknown or suspected (research). A negative result is required to continue being in the study.

Visit 5 - Implant placement:

Prior to surgery, pregnancy status will be confirmed verbally. An over the counter pregnancy test will be provided if pregnancy status is unknown or suspected (research). A negative result is required to continue being in the study.

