12.4. Statistical Analyses

Include analysis of primary efficacy endpoints, secondary endpoints, safety analyses, and any planned interim analyses

The outcomes of the histologic and clinical parameters will be summarized with the sample size, mean, standard deviation, median, minimum and maximum. The significance of variation in the mean with group BioOss collagen or Ossix Bone will be assessed with two-sample *t*-testing. The significance of variation in the group effect with another variable will be assessed with an interaction term in a linear model. All statistical testing will be two-sided with a significance level of 5%. Spearman rank and Pearson correlations between clinical parameters and histologic parameters will be analyzed as well. All statistical analyses will be done with statistical software.

References:

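### The comparison of change in ridge height ignores the dehiscence recorded at extraction; a prespecified adjustment would protect precision at a cost of one degree of freedom

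*Combined protocol and SAP*

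**What the plan says.** **Eligibility.** The inclusion criteria (section 6.2) admit a "dehiscence of the buccal or lingual bony plate of the tooth socket extending no more than 50% of the total depth of the socket". After extraction, section 8.8 (Visit 2) applies the limit again to the buccal plate: "If the buccal plate is intact, defined as no bony dehiscence greater than 50% of the socket depth, the patient will remain enrolled". Above the limit, "if the buccal plate integrity has not been maintained (bony dehiscence >50%) the patient will be exited from the study". The word intact therefore covers everything from no defect to a defect of half the socket depth.

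**Baseline record.** Section 8.8 (Visit 2) then says "After extraction, the number of bony walls in each socket will be recorded along with the presence of any bony dehiscences or fenestrations". The next step described is debridement and grafting. Presence is named; depth, extent and the plate concerned are not.

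**Outcome.** The secondary outcomes are "change in ridge width; change in buccal ridge height, and change in lingual ridge height". Height is read through two stent holes, "one hole directly above the facial bony crest and another hole directly above the lingual bony crest". The baseline reading is taken before the tooth is extracted, and the second at the same locations at implant surgery (Visit 5).

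**Analysis.** Section 12.4 states: "The significance of variation in the mean with group BioOss collagen or Ossix Bone will be assessed" by a two-sample t-test. A linear model follows, but only to test whether the group effect varies with some other variable, left unnamed.

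**Allocation.** Section 10.1 describes simple 1:1 randomization from 22 sealed envelopes per arm. An envelope is drawn before the surgical appointment, and the surgeon is not blinded.

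**The concern.** Height change is a change in the position of the bony crest. A plate that has lost part of its crest and one that has not may well be expected to change by different amounts over the healing period. If so, dehiscence is a prognostic baseline factor for exactly these two outcomes. The plan collects it and then does not use it in the group comparison.

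Two things follow. The spread between socket types goes into the error term, so the t-test has less power than the data allow. And with 14 evaluable patients per arm, a few more dehisced sockets in one arm can shift that arm's mean for reasons unrelated to the graft material. An unadjusted analysis cannot separate the two.

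**Working it through.** **The plan's own figure.** No sample size or power is stated for ridge height. The only power figure, 88.5% in section 12.2, is for percentage of new bone by Mann-Whitney U test with 14 per group and a 1 SD difference. Recomputed two-sided, those inputs give 72.1% (t-test), 70.0% (Mann-Whitney, efficiency 0.955) or 68.2% (simulated Mann-Whitney), not 88.5%. That is a separate matter and nothing below depends on it.

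**Inputs from the documents.** 14 evaluable and 22 enrolled per arm (12.2); 1:1 allocation (10.1); two-sided 5% tests (12.4).

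**Assumed inputs, because the documents give none.** Dehiscence prevalence q = 20%, 35%, 50%. Difference in mean height change between dehisced and other sockets, b = 0.5, 1.0, 1.5 residual SD; for a two-sided test its sign does not matter. True material effect 1 residual SD; normal residuals.

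**Step 1: loss of precision.** Ignoring dehiscence raises the variance from 1 to 1 + q(1-q)b².
- Mildest case, q = 0.2 and b = 0.5: 1 + 0.16 × 0.25 = 1.04. SD 1.02; effect 1/1.02 = 0.98 SD.
- Strongest case, q = 0.5 and b = 1.5: 1 + 0.25 × 2.25 = 1.5625. SD 1.25; effect 1/1.25 = 0.80 SD.

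**Step 2: power by simulation** (20,000 runs per setting, 14 per arm), unadjusted t-test / linear model with dehiscence yes/no, in percent:

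| Prevalence | b = 0.5 | b = 1.0 | b = 1.5 |
|---|---|---|---|
| 20% | 70.5 / 70.4 | 66.4 / 71.1 | 58.1 / 69.8 |
| 35% | 70.1 / 70.3 | 63.3 / 70.5 | 54.6 / 70.2 |
| 50% | 69.3 / 70.2 | 62.2 / 70.4 | 52.7 / 69.9 |

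With 22 per arm the range is 74-89% unadjusted and 89-90% adjusted.

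**Step 3: chance imbalance.** Its contribution to the between-arm difference has SD b × √(2q(1-q)/14).
- Mildest: 0.5 × √(0.32/14) = 0.076 residual SD.
- Strongest: 1.5 × √(0.5/14) = 0.28 residual SD.

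For comparison, the standard error from residual variation alone is √(2/14) = 0.38 residual SD.

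**Step 4: type I error.** Over all simulated trials it is 4.7-5.3%, adjusted or not. Among trials in which the arms differ by 4 or more dehisced sockets:

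| Per arm | Share of trials | Unadjusted error | Adjusted error |
|---|---|---|---|
| 14 | 9-19% | 6.5-14.8% | 4.2-5.6% |
| 22 | 18-30% | 5.7-11.6% | 4.7-5.3% |

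**Step 5: cost.** Residual degrees of freedom at 14 per arm go from 28 - 2 = 26 to 28 - 3 = 25. At b = 0.5 and q = 20% the power difference is 0.1 point (70.5% against 70.4%).

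**The case against.** The strongest reply is that a t-test in a randomized trial is valid without covariates, and that adjustment is an efficiency choice on two secondary outcomes for which the plan claims no power. The first part stands. A reader might infer that unadjusted analysis inflates the false-positive rate; it does not. The standard error already contains the variation from dehiscence, and overall error stays near 5%. What remains is lost precision, and error conditional on an imbalance that has actually occurred.

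A second reply is that section 12.4 does foresee a linear model with another variable. It does, but a test of interaction is not an adjusted estimate of the group difference, and dehiscence is not named.

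Other inferences are tempting and not supported:
- **That dehisced sockets gain height because the defect fills.** Baseline height is read before extraction and before the socket is inspected. A plate lost during extraction would then show extra loss, whereas a pre-existing defect might fill. Nor does section 8.8 say whether the stent hole lies over the defect. The direction is unknown, and a single term could pool opposite effects, which would reduce the gain from adjusting.
- **That plates dehisced by more than half are compared with intact ones.** Section 6.2 excludes them for either plate, and the post-extraction check exits patients when the buccal plate exceeds the limit.
- **That randomization should have been stratified on dehiscence.** The envelope is drawn before the surgical appointment, so the post-extraction finding is not available at that point.
- **That percent extent is already in hand.** The post-extraction check is a yes/no threshold on the buccal plate only. Extent for each plate would be a new measurement.

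Finally, wall count and buccal plate thickness are also recorded and might be prognostic. That is fair. Dehiscence is proposed because it is directly a defect of the crest being measured, not because the documents show it to be the best covariate.

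**Conclusion.** The point holds as a matter of efficiency and of protection against an unlucky allocation, not of validity. The plan records a plausible prognostic factor for ridge height and specifies no use of it in comparing the materials.

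Under the assumed range, with 14 per arm, ignoring dehiscence costs between nothing and about 17 points of power (52.7% against 69.9% at the extreme). The loss shrinks towards zero if dehiscence is rare or weakly related to height change. The prevalence, the effect and the residual SD are all assumptions, so these figures show what is possible, not what to expect. The conclusion concerns only change in buccal and lingual ridge height; the primary histologic outcomes are outside it.

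**What to change.** In section 12.4, prespecify the analysis of change in buccal and in lingual ridge height as a linear model with treatment group and recorded dehiscence (present/absent, for the plate concerned where noted). Report the adjusted group difference with its 95% CI, and keep the unadjusted two-sample t-test as a sensitivity analysis. Keep this separate from the interaction model, and name the variable intended there.

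In section 8.8 (Visit 2), state that dehiscence is recorded before the graft is placed, and preferably for which plate. The order of the text implies the timing. Because allocation is already known and the surgeon is unblinded, it should be explicit.

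The cost is one degree of freedom and one model term, with no added patients or procedures. If no socket is dehisced, the term drops out and the model reduces to the t-test. Recording the extent for each plate is optional and would be an added measurement. The choice should be fixed before outcome data are seen, since a covariate chosen afterwards carries little weight.

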9.1. Acquisition and accountability

State how the study intervention and control product will be provided to the investigator. Describe plans about how and by whom the study intervention will be distributed, including participation of a drug repository or pharmacy, and plans for disposal of expired or return of unused product.

9.2. Formulation, Appearance, Packaging, and Labeling

Describe the formulation, appearance, packaging, and labeling of the study intervention and control product, as supplied. Information in this section can usually be obtained from the IB or the package insert, or device labeling. This section should include the name of the manufacturer of the study intervention and control product.

9.3. Product Storage and Stability

Describe storage and stability requirements (e.g., protection from light, temperature, humidity) for the study intervention and control product. For studies in which multi-dose vials are utilized, provide additional information regarding stability and expiration time after initial use (e.g., the seal is broken).

9.4. Preparation

Describe the preparation of the study intervention and control product, including any preparation required by study staff and/or study participants. Include thawing, diluting, mixing, and reconstitution/preparation instructions in this section. For devices, include any relevant assembly or use instructions.

10. Study Intervention Additional Details

10.1. Measures to Minimize Bias: Randomization and Blinding

This section should contain a description of randomization and blinding procedures (if applicable to the study design). It should include a description or a table that describes how study participants will be assigned to study groups, without being so specific that blinding or randomization might be compromised. Plans for the maintenance of trial randomization codes and appropriate blinding for the study should be discussed. The timing and procedures for planned and unplanned breaking of randomization codes should be included. Include a statement regarding when unblinding may occur and who may unblind. Provide the criteria for breaking the study blind or participant code. Discuss the circumstances in which the blind would be broken for an individual or for all participants (e.g., for serious adverse events (SAEs)). Indicate to whom the intentional and unintentional breaking of the blind should be reported.

22 envelopes will be prepared for each arm in a simple randomization 1:1 ratio, sealed and shuffled. The faculty staffing the procedure will draw an envelope from the stack prior to the surgical procedure appointment. Since the outcome of the study is the histologic healing, blinding of the surgeon is not necessary.

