- Notification to the patient that inclusion in the study is voluntary and conditional upon satisfying the inclusion and exclusion criteria.

Patient will be given the opportunity during the appointment to ask any question that he/she may have. Following an informational discussion with the prospective subject, consent will be obtained within 2 weeks. This is up to the discretion of the patient. If the patient would like to become a subject for entry into the study, he or she can do so immediately, or can consider it for up to 2 weeks (must be prior to extraction).

Visit 2 – Extraction with ridge preservation using either 90% bovine derived xenograft granules and 10% porcine collagen (Bio-Oss® Collagen, Geistlich, Inc.) or a resorbable sponge-like matrix of 80% hydroxyapatite and 20% sugar ross-linked porcine collagen (Ossix™ Bone, Datum Dental Ltd).

The patient will be assigned to either group by simple randomization with a 1:1 ratio

If the patient has agreed to participate in the study, informed consent will be obtained and documented on a written consent form. If not, standard care treatment will be provided to the patient, but the patient would not be included in the study.

On the day of the planned extraction, the medical history will be updated.

Pregnant women or women intending to become pregnant during the study period: Prior to dental surgery, females of child-bearing age are asked verbally if there is any possibility that they are pregnant. If not, we proceed with surgery and no pregnancy test is done. If the woman states that there is a possibility that she is pregnant, an over the counter urine pregnancy test to rule pregnancy in or out will be provided. Use of the urine pregnancy test is only done if she says she may be pregnant. [If needed: Urine pregnancy test will be provided to female subjects in the graduate periodontics clinic of UTHSCSA and a negative result is required to enter the study.]

Impressions of the arch with the tooth to be extracted in place will be taken prior to extraction and poured in stone to obtain initial study casts (research). If the tooth to be extracted is fractured, a wax-up of the tooth will be made before the stent is fabricated (research).

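### The envelope is drawn before the surgical appointment but enrolment is settled after extraction, and nothing keeps the envelope sealed in between

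*Combined protocol and SAP*

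**What the plan says.** **Allocation (section 10.1).** The stack is described as follows: "22 envelopes will be prepared for each arm in a simple randomization 1:1 ratio, sealed and shuffled". The draw is then given a time and a person: "The faculty staffing the procedure will draw an envelope from the stack prior to the surgical procedure appointment". The same section waives blinding of the surgeon because the outcome is histologic.

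**Visit 2 (section 8.8).** The 1:1 assignment is mentioned under this visit but is not placed relative to extraction. Consent may be given at once or considered for up to two weeks, as long as it precedes extraction, and written consent is described under this visit: "If the patient has agreed to participate in the study, informed consent will be obtained and documented on a written consent form". The baseline reading comes next: "Prior to tooth extraction, the clinical measuring stent will be placed and measurements of ridge width and ridge height will be taken and recorded". Enrolment is settled later still: "Following tooth extraction, a final determination of enrollment into the study will be conducted based on the integrity of the buccal bone wall plate". The exit rule is numeric: "if the buccal plate integrity has not been maintained (bony dehiscence >50%) the patient will be exited from the study".

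**What is not stated.** No section says when a drawn envelope is opened, who opens it, that it stays sealed until the socket decision is recorded, who makes that decision, or whether an exited patient's envelope is used up or returned.

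**The concern.** Concealment has to last until the patient is irrevocably in the trial. Here the draw has a stated time, and it falls before the step that settles who is in. If the envelope has been opened by then, two things are exposed.

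- **The socket decision.** A socket near the 50% limit could be kept or exited according to the graft that comes next. The person who draws the envelope also staffs the procedure.
- **The baseline ridge reading.** Baseline width and height enter the change scores for the secondary outcomes directly, so a reading taken with the arm known passes straight into them.

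The reason given for not blinding the surgeon concerns the histologic outcome. It does not address who is enrolled, or the ridge measurements.

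**Working it through.** The plan gives no figure on this point to reproduce, so the check is of sequence first and then of plausible size.

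**1. Order of events**

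| Step | Time stated | Section |
|---|---|---|
| Envelope drawn | Before the surgical appointment | 10.1 |
| Written consent | Any time up to extraction; described under Visit 2 | 8.8 |
| Baseline ridge width and height | Visit 2, before extraction | 8.8 |
| Final enrolment decision | Visit 2, after extraction | 8.8 |
| Graft placed | Visit 2, after that decision | 8.8 |
| Envelope opened | Not stated | none |

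The draw precedes the baseline reading and the enrolment decision, and may precede written consent.

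**2. Bias from selective exits**

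The documents give no exit rate and no difference in prognosis, so every input here is assumed. Let *p* be the share of sockets that would heal worse, *g* the gap in SD, *e* the share exited in an arm, and *f* the share of exits that are poorer sockets. The mean of the retained patients is −*g*(*p* − *f·e*)/(1 − *e*), and the bias is the difference between arms.

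Near worst case (*f* = 1, all extra exits in one arm):

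| *p* | Exits, arm A v B | Bias, *g* = 0.5 | Bias, *g* = 1 |
|---|---|---|---|
| 0.05 | 0 v 0.05 | 0.025 | 0.050 |
| 0.10 | 0 v 0.10 | 0.050 | 0.100 |
| 0.20 | 0.10 v 0.20 | 0.056 | 0.111 |

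Last cell: arm A is −(0.20 − 0.10)/0.90 = −0.111, arm B is 0/0.80 = 0, difference 0.111 SD. The 5 to 10 point gap in exits is 22 × 0.05 = 1.1 to 22 × 0.10 = 2.2 patients.

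Milder case (*f* = 0.5): bias 0.012 to 0.044 SD.

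**3. Effect on the two-sided 5% test**

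The planned test is a two-sample *t*-test (section 12.4). With a shift of *b* SD and no true difference, the rejection rate comes from the noncentral *t* distribution with noncentrality *b*/√(1/n₁ + 1/n₂) and n₁ + n₂ − 2 degrees of freedom.

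- At 14 per arm, the number section 12.2 requires, shifts of 0.025, 0.050, 0.100 and 0.111 give 5.05%, 5.19%, 5.75% and 5.92%.
- The largest shift, with exits removed from 22 per arm: 22 × 0.90 = 19.8 and 22 × 0.80 = 17.6, giving about 6.3%. After the planned 30% dropout: 19.8 × 0.70 = 13.9 and 17.6 × 0.70 = 12.3, giving about 5.9%.
- If 22 per arm means patients past the socket check, 22 × 0.70 = 15.4 complete, and the largest shift gives about 6.0%.
- Milder case: about 5.0 to 5.2%.

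**4. Baseline ridge reading**

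Readings are to the nearest 0.5 mm. Assume one 0.5 mm step is shifted in 1 to 4 of 22 patients in one arm. The mean change then moves by 0.5 × 1/22 = 0.02 mm to 0.5 × 4/22 = 0.09 mm. The documents give no SD for ridge change, so this cannot be put on a standardised scale.

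**The case against.** **This is a silence, not an error.** The envelopes are sealed and the text says they are drawn, not opened. The Visit 2 assignment line fits opening just before grafting. This stands against any claim that concealment fails. A reader might infer that the operator knows the arm when judging the socket; the documents do not show that. It does not remove the point, because section 10.1 states a time for the draw and that time is earlier than it needs to be.

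**The exit rule is numeric.** It confines discretion to borderline sockets, and no motive for favouring either graft is documented. Both stand, and both keep the effect small.

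**The baseline reading is protected.** It is taken through stent holes with a caliper, and section 10.2 says faculty can verify measurements. This is partial protection only, because the staffing faculty member also draws the envelope. The reading bears on secondary outcomes only.

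**Stronger readings that do not hold.**
- A reader might infer that the completer analysis in section 12.3 hides the exits. An exited patient receives standard care and no study graft, so there is no study-graft outcome under any analysis set. What is missing is a statement that exits are reported.
- A reader might count the pregnancy check as another exposed decision. It rests on the patient's answer and, if needed, a urine test, which leaves staff little room to act on the arm.
- A reader might infer that the draw precedes consent. It can, but consent may also be given at Visit 1.
- A reader might take the error as high as 6.5%. That requires the largest shift with 22 analysed per arm, which does not fit the exits that produce the shift or the planned dropout.

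**Conclusion.** The point holds as a gap in allocation procedure. As written, the plan draws the allocation before eligibility is final, lets patients be exited afterwards, and states no rule that protects the borderline socket decision or the baseline ridge reading from knowledge of the arm. It is not a demonstrated breach of concealment.

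The likely effect is small: a bias of about 0.03 to 0.11 SD near the worst case, against a design difference of 1 SD, and a two-sided error of about 6% at most at the planned number of completers. These figures rest wholly on assumed exit rates and prognosis gaps. The case for acting is that the change is cheap and cannot be made once patients are treated. It should be made, but the trial does not stand or fall on it.

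Sections 6.2 (buccal or lingual plate) and 8.8 (buccal plate only) describe the dehiscence criterion differently. That is a separate point and adds no weight here, but those passages must be reconciled.

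**What to change.** **Full change.** Amend section 10.1 and Visit 2 in section 8.8 so that the envelope is drawn and opened only after written consent, baseline ridge measurements, extraction and the recorded dehiscence decision, immediately before grafting. Name who opens it and log the time. Exited patients are then unrandomised screen failures, use no envelope, and are reported with number and reason.

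**Minimum.** State that a drawn envelope stays sealed until the dehiscence decision is recorded, log the time of opening, and return the envelope unopened if the patient exits.

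**Cost.** Under either version both products must be on hand at each extraction and the envelope is opened during surgery. A few more patients may need to be consented if 22 per group means patients randomised after the check. At an assumed exit rate of 5 to 20%, 44 randomised sockets need 44/0.95 = 46.3 (47) to 44/0.80 = 55 consents, or 3 to 11 more than 44. If the 30% allowance in section 12.2 is meant to cover these exits, some or all of that extra falls away; the documents do not settle which reading applies.

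**Limit.** The change protects enrolment and the baseline reading only. Section 8.8 describes no masking of the ridge measurement at implant placement, and this change does not supply it.
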